1.2.3. Randomization and Blinding

Randomization will be used to minimize bias in the initial assignment of participants to intervention groups, to increase the likelihood that known and unknown participant attributes (eg, demographic and baseline characteristics) are evenly balanced across intervention groups, and to enhance the validity of statistical comparisons across intervention groups. In addition, stratification by known potentially relevant baseline characteristics that may affect study outcomes will also be used to avoid chance imbalance of these relevant variables among treatment groups. Blinded intervention will be used to reduce potential bias during data collection and evaluation of clinical endpoints.

Intervention Allocation

Procedures for Randomization and Stratification

Central randomization will be implemented in this study. At Week 0, participants will be randomly assigned to 1 of 2 intervention groups in a 1:1 ratio based on a computer-generated randomization schedule prepared before the study by or under the supervision of the sponsor. The randomization will be balanced by using randomly permuted blocks and will be stratified by clinical remission status at baseline (CDAI < 150, CDAI \ge 150), region (North America, Western Europe, rest of world) and number of prior surgeries (1 surgery versus > 1 surgery, with the qualifying surgery counting as 1 surgery). The IWRS will assign a unique intervention code, which will dictate the intervention assignment and matching study intervention kit for the participant.

Blinding

To maintain the study blind, the study intervention container will have a label containing the study name, study intervention number, and reference number. The study intervention number will be entered in the eCRF when the study intervention is dispensed. Each active study intervention and its matching placebo will be identical in appearance and will be packaged in identical containers. All participants will receive the same device(s), which could be either active or matching placebo at 8-week intervals to maintain treatment blinding.

The investigator will not be provided with randomization codes. The codes will be maintained within the IWRS, which has the functionality to allow the investigator to break the blind for an individual participant.

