3. SAMPLE SIZE DETERMINATION

A sample size of 370 participants (185 participants assigned to guselkumab and 185 assigned to placebo) will allow to have at least 90% power to detect 20% differences between guselkumab (30%) and placebo (50%) for endoscopic recurrence rate (primary endpoint) at Week 48, assuming a 2-sided alpha level of 0.05.

This also will allow at least 90% power to detect 17% differences between guselkumab (37%) and placebo (20%) for clinical remission without disease recurrence at Week 48, assuming a 2-sided alpha level of 0.05. This also will allow 90% power to detect 10% differences between guselkumab (10%) and placebo (20%) for disease recurrence at the main database lock, all available follow-up of all participants will be used to examine disease recurrence at the time of the primary database lock.

Endoscopic Recurrence

Assumptions for endoscopic recurrence prior to or at Week 48 were based on previous studies, as described in Table 2.

Reference*	Endoscopic Recurrence definition	Sample Size	Placebo rate	Timepoint
		-		-
Regueiro 2016	Rutgeerts \geq i2	150	60%	76 weeks
Yamamoto 2007	Rutgeerts \geq i2	20	70%	52 weeks
Marteau 2006	Rutgeerts \geq i2	47	64%	24 weeks
Rutgeerts 2005	Rutgeerts \geq i2	33	78.8%	52 weeks
Hanauer 2004	Rutgeerts \geq i2	40	64%	104 weeks
Lochs 2000	Rutgeerts \geq i2	166	50%	72 weeks
Ewe 1999	Rutgeerts \geq i2	40	70%	52 weeks
Hellers 1999	Rutgeerts \geq i2	66	58%	52 weeks

Table 2:	Endoscopic	Recurrence,	Placebo	Group
----------	------------	-------------	---------	-------

* References are provided in the protocol.

Based on these data above, the endoscopic recurrence rates are assumed to be 50% for placebo and 30% for guselkumab.

To accommodate other potential scenarios, power was calculated based on different assumptions as listed in Table 3.

Event rate at Week 48 for endoscopic recurrence in placebo group	Event rate at Week 48 for endoscopic recurrence in guselkumab group	Difference to be detected	Power
50%	30%	20%	97.7%
50%	25%	25%	99.9%
50%	35%	15%	83.3%
45%	25%	20%	98.3%
40%	20%	20%	98.9%
60%	30%	30%	>99.9%

 Table 3:
 Power to Detect a Treatment Effect Based on Different Scenarios in Endoscopic Recurrence

Clinical Remission without Disease Recurrence

Based on data from PREVENT (20% for placebo, and 36.7 for Infliximab), the rates of clinical remission without disease recurrence are assumed to be 20% for placebo and 37% for guselkumab.

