To accommodate other potential scenarios, power was calculated based on different assumptions as listed in Table 4:

Table 4:	Power to Detect a Treatment Effect Based on Different Scenarios in Clinical Remission without
	Disease Recurrence

Event rate at Week 48 for clinical remission without disease recurrence in placebo group	Event rate at Week 48 for clinical remission without disease recurrence in guselkumab group	Difference to be detected	Power
20%	35%	15%	90.0%
20%	36%	16%	93.1%

Disease Recurrence

Assumptions for disease recurrence were based on previous studies, as described in Table 5.

Reference*	Disease Recurrence definition	Sample Size	Placebo rate	Timepoint
Regueiro 2016	$CDAI \ge 200$ and 70 point increase	150	20%	76 weeks
Ng 2009	Symptoms related to CD associated with endo, lab or radiologic findings	99	28%	52 weeks
Yamamoto 2007	CDAI ≥ 150	20	35%	52 weeks
Rutgeerts 2005CDAI > 250 or need for rescue medical therapy		40	37.5%	54 weeks
Prantera 2002 CDAI >150, confirmed by endoscopy		22	10.5%	52 weeks
Lochs 2000 CDAI >250 or CDAI > 200 with a 60 point increase		166	31.4%	72 weeks
Hellers 1999 CDAI > 200		66	31%	52 weeks
Ewe 1999 CDAI > 200, rise of 60 points		40	28%	52 weeks
Olaison 1992	92 CDAI > 150 or HBI > 4		37%	52 weeks

 Table 5:
 Disease Recurrence, Placebo Group

* References are provided in the protocol.

For this endpoint, all follow-up data available at the primary DBL, including beyond one year when available, will be used. Based on this, as well as these data above, the disease recurrence rates are assumed to be 20% for placebo and 10% for guselkumab.

To accommodate other potential scenarios, power was calculated based on different assumptions as listed in Table 6.

Event rate at Week 48 for disease recurrence in placebo group	Event rate at Week 48 for disease recurrence in guselkumab group	Difference to be detected	Power
20%	10%	10%	90.0%
	8%	12%	98.5%
25%	15%	10%	80.9%
	10%	15%	99.7%
30%	15%	15%	98.5%

 Table 6:
 Power to Detect a Treatment Effect Based on Different Scenarios in Disease Recurrence

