Accrual time used here is 18 months, total time used here is 30 months. It is expected median follow-up time available at the time of, and thus incorporated in, the main database lock is approximately 18 months. Assuming non-uniform accrual pattern: 25% of participants will be enrolled in the first 6 months, 35% of participants will be enrolled in the next 6 months, and 40% will be enrolled in the last 6 months. Assuming dropout rate is 15% annually. Average duration of follow-up is expected to be approximately 20 months.

Analysis Sets	Description
Randomized	The randomized analysis set includes all participants who were
	randomized in the study.
Full Analysis Set (FAS)	All randomized participants.
	Participants in the FAS will be analyzed according to their randomized study intervention regardless of the study intervention they actually received.
Safety Analysis Set	All randomized participants who receive at least 1 dose of study intervention.
	Participants in the Safety Analysis Set will be analyzed according to the study intervention they actually received.
Pharmacokinetics Analysis Set	All randomized participants who receive at least 1 dose of study intervention and have at least one valid blood sample drawn postbaseline for PK analysis.
	Participants in the PK Analysis Set will be analyzed according to the study intervention they actually received.
Immunogenicity Analysis Set	All participants who received at least 1 dose of study intervention and have appropriate samples for anti-drug antibody detection.
	Participants in the Immunogenicity Analysis Set will be analyzed according to the study intervention they actually received.

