5.3.3. Analysis Methods

5.3.3.1. Estimator (Analysis) of the Primary Estimand

The analyses will be based on the Full Analysis Set (FAS), which includes all randomized participants. Participants will be analyzed according to the intervention group to which they were randomized regardless of the study intervention they actually received.

To compare the guselkumab versus placebo group for the primary endpoint, the Cochran Mantel Haenszel chi-square test (2-sided) will be used with stratification of clinical remission status at baseline (CDAI < 150, CDAI \ge 150), region (North America, Western Europe, rest of world) and number of prior surgeries (1 surgery versus > 1 surgery, with the qualifying surgery counting as 1 surgery). The study will be considered successful if the test of the primary endpoint is positive at the 0.05 significance level.

After accounting for the ICE strategies, missing data will be imputed by multiple imputation.

Multiple imputation will be used for imputing missing data under the assumption that the data are MAR. The analysis will impute the missing Rutgeerts score at Week 48 using the analysis method and ancillary variables as described in Table 8. The responses at Week 48 will be derived from the imputed datasets and combined for analysis.

Variable	MI specification	Analysis method/Summary statistics
Rutgeerts score at Week 48	Multiple imputation with monotone regression of total scores	 MIdataset1 (N=200, Seed=5748941) Imputation variables: Rutgeerts score at Week 48 Ancillary variables: Treatment group, and history of primary non-response to at least one approved ADT (Yes, No), clinical remission status at baseline (CDAI < 150, CDAI ≥ 150), region (North America, Western Europe, rest of world) and number of prior surgeries (1 surgery versus > 1 surgery, with the qualifying surgery counting as 1 surgery)

 Table 8:
 Multiple Imputation Methods for Rutgeerts Score at Week 48

The number and percentage of participants who experienced any ICE prior to Week 48 will be summarized by the type of ICE.

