Summaries of median survival time and interquartile range of survival time by treatment group will be provided. The log-rank test will be used to compare disease recurrence distribution between the two treatment groups. The Kaplan-Meier method will be used to estimate the distribution of disease recurrence for each treatment. The treatment effect (hazard ratio) and its two-sided 95% confidence intervals are to be estimated using Cox regression model with treatment and stratification factors. Participants who have not achieved disease recurrence during the main study period at the database lock will be censored at the last visit. Participants without any post-baseline follow-up will be censored at randomization.

Estimators of Abdominal Pain Free at Week 48

Summaries of the proportion of participants that achieve abdominal pain free by treatment group will be provided. To compare the guselkumab versus placebo group for the first secondary endpoint, the CMH chi-square test (2-sided) will be used with stratification of clinical remission status at baseline (CDAI < 150, CDAI \ge 150), region (North America, Western Europe, rest of world) and number of prior surgeries (1 surgery versus > 1 surgery, with the qualifying surgery counting as 1 surgery).

After accounting for the ICE strategies, missing data will be imputed by multiple imputation. Multiple imputation will be used for imputing missing data under the assumption that the data are MAR. The analysis will impute the missing Rutgeerts score at Week 48 using the analysis method and ancillary variables as described in Table 12. The responses at Weeks 48 will be derived from the imputed datasets and combined for analysis.

Variable	MI specification	Analysis method/Summary statistics
AP score at Week 48	Multiple imputation with monotone regression of total scores	 MIdataset1 (N=200, Seed=5748941) Imputation variables: AP score at Week 48 Ancillary variables: Treatment group, baseline Rutgeerts score, history of primary non-response to at least one approved ADT (Yes, No), clinical remission status at baseline (CDAI < 150, CDAI ≥ 150), region (North America, Western Europe, rest of world) and number of prior surgeries (1 surgery versus > 1 surgery, with the qualifying surgery counting as 1 surgery)

Table 12:	Multiple Imputation Methods for AP Score at Weeks 48
-----------	--

Estimators of Recurrence of Symptoms

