Time-to-event endpoints will be summarized with median survival time and interquartile range of survival time by treatment group. Kaplan-Meier curves will be provided for time-to-event endpoints as well. Treatment comparisons will be performed using the log-rank test stratified by clinical remission status at baseline (CDAI < 150, CDAI \ge 150), region (North America, Western Europe, rest of world) and number of prior surgeries (1 surgery versus > 1 surgery, with the qualifying surgery counting as 1 surgery).

Continuous Endpoints

The ICEs specified as following will be applied to each of the above continuous endpoints, ie, if a participant has an ICE in categories 1-4, last available values will be assigned from the point of ICE onward (i.e., no change from baseline). For participants experiencing an ICE 5 or ICE 6, their observed values will be used, if available. Note that the application of ICE categories 1-4 overrides that of ICE 6 and ICE 6. This means that for a participant with an ICE in categories 1-4 baseline values will be assigned from the point of ICE onward (ie, no change from baseline), regardless of whether the participant has had an ICE 5 or ICE 6.

To account for the missing data for continuous endpoints of change from baseline measured at more than one post-baseline visit (after applying the ICEs), a Mixed-Effect Model Repeated Measures (MMRM) will be used, under the assumption of missing at random (MAR), to test the difference between treatment groups. In MMRM, missing data will not be imputed, but rather missing data will be accounted for through correlation of repeated measures in the model. Additionally, if the MMRM normality assumption is in question, an appropriate transformation may be implemented before fitting the MMRM model.

The explanatory variables of the MMRM model will include treatment group, visit, applicable baseline score, clinical remission status at baseline (CDAI < 150, CDAI \ge 150), region (North America, Western Europe, rest of world) and number of prior surgeries (1 surgery versus > 1 surgery, with the qualifying surgery counting as 1 surgery), an interaction term of visit with treatment group, and an interaction term of visit with applicable baseline score.

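### Minor: the log-rank tests for hierarchy steps 3 and 5 omit the randomisation strata, so they are valid but gradually conservative as the strata become prognostic

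*SAP*

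**What the plan says.** Randomisation uses permuted blocks within 2 x 3 x 2 = 12 cells: baseline CDAI below 150 or not, three regions, and one or more than one surgery. SAP Section 1.2.3 justifies this as "stratification by known potentially relevant baseline characteristics that may affect study outcomes".

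The analyses use these factors as follows:

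- **Steps 1, 2, 4 and 6 (binary).** The CMH "chi-square test (2-sided) will be used with stratification of clinical remission status at baseline" and the other two factors (Section 5.3.3.1). Section 5.4.1.3 does the same for the secondary endpoints.
- **Exploratory endpoints (Section 5.5.2).** The CMH test is stratified, and for time-to-event endpoints "Treatment comparisons will be performed using the log-rank test stratified by clinical remission status at baseline", region and surgeries.
- **Step 3, time to disease recurrence (Section 5.4.1.3).** "The log-rank test will be used to compare disease recurrence distribution between the two treatment groups". No strata are named. In the same paragraph the hazard ratio and its interval are "estimated using Cox regression model with treatment and stratification factors".
- **Step 5, time to recurrence of symptoms (Section 5.4.1.3).** The same two sentences, still referring to disease recurrence.

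Nothing else extends the strata to steps 3 and 5. The general considerations in Section 5.1 are silent, and Section 5.5.2 covers only the endpoints listed in Section 5.5.1. Protocol Section 9.4.3 also gives the log-rank test for disease recurrence without strata.

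**The concern.** Two confirmatory tests ignore factors that govern the randomisation and nearly every other comparison, so an exploratory time-to-event endpoint has a more fully specified test than a confirmatory one. When allocation is balanced within prognostic strata and the test ignores them, the variance used is too large. The test then rejects too rarely under the null and loses power under the alternative. Step 3 gates steps 4 to 6, so power lost there is passed down the hierarchy. The p-value and the hazard-ratio interval also come from different models and can disagree on significance.

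**Working it through.** **1. The SAP's own power for step 3.** The inputs are from SAP Section 3: 185 per arm, two-sided 0.05, accrual 25/35/40% over three six-month periods, 30 months in total. "Assuming dropout rate is 15% annually". Table 6 heads its column "Event rate at Week 48 for disease recurrence in placebo group", with 20% against 10%. Event times are taken as exponential.

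- Monthly hazards, with 48 weeks = 11.04 months: placebo -ln(0.80)/11.04 = 0.02021; guselkumab -ln(0.90)/11.04 = 0.00954; dropout d = -ln(0.85)/12 = 0.01354.
- HR = ln(0.90)/ln(0.80) = 0.472.
- Event probability for entry at month a: h/(h+d) x [1 - exp(-(h+d)(30-a))]. Averaged over accrual this is 0.2906 and 0.1517.
- Events: 185 x 0.2906 + 185 x 0.1517 = 81.8.
- Freedman: sqrt(81.8) x (1-0.472)/(1+0.472) - 1.96 = 3.24 - 1.96 = 1.28, power 90.0%. **Stated: 90.0%.**
- Schoenfeld: sqrt(81.8)/2 x 0.750 - 1.96 = 1.43, power 92.4%. With the rates read at 12 months: 76.2 events, 90.6%.
- Mean follow-up: 30 - (0.25x3 + 0.35x9 + 0.40x15) = 20.1 months, against about 20 stated.

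These formulas contain no strata, so the stated power belongs to the test as written.

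**2. Effect of omitting the strata (simulation).** The design inputs are as above, with blocks of 4 in each of the 12 cells and marginal Week 48 rates held at 20%/10% (20% in both arms for size). The following are assumed, because the documents give no values. Shares: CDAI at or above 150 30%, regions 40/35/25%, more than one surgery 35%. Hazard ratios for CDAI; region (highest against lowest); surgery: modest 1.5; 1.4; 1.5. Intermediate 2; 1.7; 2. Strong 2.5; 2; 2.5. Very strong 4; 3; 3. Their product is the ratio between extreme cells. Size used 35,000 trials (SE 0.1 point) and power 10,000 (SE 0.3). Changes are taken before rounding.

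| Effects | Extreme-cell HR | Size %, unstratified / stratified log-rank | Power %, unstratified / stratified log-rank | Change from stratifying (points) | Planned Cox interval excludes 1 (%) |
|---|---|---|---|---|---|
| None | 1 | 4.7 / 4.8 | 91.6 / 90.8 | -0.8 | 91.6 |
| Modest | 3.2 | 4.6 / 5.0 | 91.3 / 91.1 | -0.3 | 91.7 |
| Intermediate | 6.8 | 4.4 / 5.2 | 90.7 / 91.2 | +0.6 | 92.1 |
| Strong | 12.5 | 3.7 / 4.9 | 90.5 / 91.8 | +1.3 | 92.8 |
| Very strong | 36 | 2.9 / 5.1 | 89.5 / 93.4 | +3.9 | 94.5 |

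Repeat runs put the unstratified size at 4.1-4.3% (modest), 3.8% (strong) and 3.0% (very strong). Stratifying breaks even on power at roughly a 4- to 5-fold ratio between extreme cells.

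A second pattern applies one hazard ratio per step to all three factors. Region counts as two steps, so extreme cells differ by that ratio to the fourth power; 40% are taken to have more than one surgery. Unstratified size is 4.4% at 1.5 per step, 3.8% at 2 and 2.3% at 3. The power change from stratifying is -0.4, +2.2 and +8.9 points (the last with rates at 48 weeks, the others at 12 months).

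**3. Agreement of p-value and interval.** In the order of the table, log-rank significance and the Cox 95% interval disagree in 0.6/1.5/2.3/3.1/5.6% of trials as planned. With a stratified log-rank and the same Cox model they disagree in 2.3/2.1/2.2/2.4/2.3%. No trial had estimates of opposite sign with either result significant.

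**4. With censoring at Week 48 cross-over (Section 5.4.1.1).** Section 3 says "the endoscopic recurrence rates are assumed to be 50% for placebo and 30% for guselkumab". Of participants free of disease recurrence at Week 48, (50-20)/(100-20) = 37.5% on placebo and (30-10)/(100-10) = 22.2% on guselkumab are then censored. This treats every disease recurrence as also an endoscopic one, although fistulas and abscesses count without endoscopy, and it ignores the optional Week 24 cross-over. Events fall to 69-72. The power change is -1.2/-0.8/+0.4/+1.2/+4.0 points. Disagreement is 0.9/1.7/2.5/3.6/6.3% as planned and 2.9-3.3% with the log-rank stratified.

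Step 5 cannot be quantified, because the documents give no event rate for it.

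**The case against.** The strongest defence is that an unstratified log-rank test for inference with a covariate Cox model for estimation is a coherent plan. The SAP gives each a role, and if they disagree the prespecified test decides the hierarchy. That stands: no decision rule is ambiguous.

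The harm also rests on stratum effects that the documents do not supply. Section 1.2.3 claims only that such factors may matter. Entry requires a CDAI below 200, so the upper CDAI stratum spans only 150 to 199, and low-risk patients are excluded. With no or modest effects the planned test is slightly more powerful than the stratified one. This stands too, and it keeps the point minor.

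A reader might infer that the Cox model should also be stratified, so that p-value and interval share one model. The figures do not support that. The planned covariate model has about nominal size (4.3-5.7% across runs) and is at least as powerful as either log-rank test in every setting. A stratified Cox interval excludes 1 in 90.6/90.8/91.0/91.5/93.1% of trials, which is 0.9 to 1.4 points fewer than the planned model.

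Nor does the protocol need amending. Its Sections 9.4.2 and 9.4.3 give the CMH tests without strata as well, and Sections 9 and 9.4 leave technical detail to the SAP.

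**Conclusion.** The inconsistency is real and minor. A reader might infer inflated type I error or unsupported power. Neither follows: the test is valid, its simulated size does not exceed 5% beyond simulation error, and the stated 90.0% reproduces for it.

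What remains is conservatism that grows gradually with the prognostic strength of the strata and has no threshold. In the main pattern it costs roughly 1 to 4 points of power when extreme cells differ 12.5- to 36-fold. The more extreme second pattern (3 per step, an 81-fold difference) costs more, so the true size is not identified from the documents. The result rests on assumed stratum shares and effects, exponential times and the Section 3 accrual and dropout figures.

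A drafting omission is likely: the SAP added strata to the protocol's CMH tests but carried the log-rank sentence over unchanged, then pasted it into step 5 with the wrong endpoint name. A deliberate choice cannot be excluded.

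**What to change.** In the step 3 and step 5 paragraphs of SAP Section 5.4.1.3, specify a log-rank test stratified by baseline clinical remission status, region and number of prior surgeries, as in Section 5.5.2. In the step 5 paragraph, name recurrence of symptoms as the endpoint. Keep the planned covariate-adjusted Cox model for the hazard ratio and interval. If exact agreement between p-value and interval is wanted, test with the treatment term of that Cox model instead. If the unstratified test is intended, say so and give the reason.

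The edit is one sentence in each paragraph; the sample size and the protocol are unchanged. The costs are:

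- about 0.3 to 1.2 points of power if the factors are weakly or not prognostic;
- sparse cells: the smallest expects 370 x 0.30 x 0.25 x 0.35 = 9.7 participants under the assumed shares, and 2.6 to 4.4 of the 12 cells have fewer than five events and add little information;
- log-rank p-value and Cox interval still disagreeing in about 2-3% of trials, which is more often than now if the strata are weak and less often if they are strong.
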